7 SIGNATURES PAGE

APPENDIX 1 SUMMARY OF EFFICACY ANALYSES

Endpoint	Analysis Set	Statistical Method	Model/ Covariates	Missing Data
Mean efficacy change from Baseline	FAS	ANCOVA	Skin type group / Baseline mean	Excluded
Treatment differences in mean efficacy change from Baseline	FAS	ANCOVA	Treatment, skin type group / Baseline mean	Excluded

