### 8.4. SAMPLE SIZE DETERMINATION

The total sample size of 96 (48 per treatment cell) completed subjects provides 92% power to detect a treatment effect of 0.7 using a two-sided test at the 0.05 significance level. The 0.7 effect size is estimated based on a previous study of similar design using the 9-point Fitzpatrick Wrinkle and Elastosis Scale.

[REDACTED]

[REDACTED]

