4.4 COVARIATES

Model-based within-treatment and between-treatment comparisons of the efficacy variables will use the corresponding baseline value as a covariate.

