6 STATISTICAL METHODOLOGY AND STATISTICAL ANALYSES

6.1 STATISTICAL HYPOTHESES

The primary efficacy variable is the change from baseline in global wrinkling at Week 12.

Specifically, the following hypothesis will be tested to assess within-treatment changes from baseline:

$$H_0: \mu_{\text{Baseline}} - \mu_{\text{Post}} \leq 0.5$$

against the one-sided alternative

$$H_1: \mu_{\text{Baseline}} - \mu_{\text{Post}} > 0.5$$

where μ_{Baseline} and μ_{Post} are baseline mean global wrinkling and post-baseline mean global wrinkling, respectively, for active mask or sham mask treatment.

The null hypothesis that two investigational product mean efficacy variable changes from baseline are equal will be tested against the alternative hypothesis that the investigational product mean efficacy variable changes from baseline are not equal.

In other words, the following hypothesis will be tested:

$$H_0: \mu_A - \mu_S = 0$$

against the two-sided alternative

$$H_1: \mu_A - \mu_S \neq 0$$

where μ_A and μ_S are the mean changes from baseline for active mask treatment and the sham mask treatment, respectively.

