6.2 STATISTICAL DECISION RULES

Superiority to baseline will be concluded if at least two of the three Expert Graders rate the active mask superior to baseline with respect to global wrinkling at Week 12 and the mean improvement score in global wrinkling for the active mask exceeds 0.5 points at Week 12, that is the lower bound of the 95% confidence interval for the mean difference is above 0.5. (Note that under 8.2.1. Analysis of Primary Variable of the protocol it incorrectly reads that superiority to baseline will be concluded if the upper bound of the 95% confidence interval for the mean difference is below -0.5.)

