6.4.2 Primary Analysis

The primary efficacy variable is the change from baseline in global wrinkling at Week 12. Scores from the 3 Expert Graders will be averaged for the baseline readings as well as the Week 12 readings before computing the change. For each subject, the change from baseline is then computed by subtracting post-baseline mean global wrinkling from baseline mean global wrinkling. The mean change from baseline for each cell will be presented together with a two-sided 95% confidence interval.

The active mask will be compared with the sham mask. Treatment means and between-treatment differences will be assessed by means of an ANCOVA model with treatment and skin type group as factors and the corresponding averaged baseline score as a covariate. The two-sided 95% confidence interval for the treatment difference will be presented. Analysis of the primary efficacy variable will be based on the average scores as well separately for the scores from each Expert Grader.

For the secondary efficacy variables, scores from the 3 Expert Graders will be averaged for the baseline as well as each post-baseline visit before computing the change. The analyses of the secondary efficacy variables will be based on average scores and will be performed as for the primary efficacy variable.

The tertiary efficacy variable is the change from baseline at Week 1, Week 4, Week 12, and Week 24 for [REDACTED]

[REDACTED]

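### SAP 6.2 does not name the interval behind its 0.5-point success bound, and the baseline-adjusted candidates are too narrow for the null in SAP 6.1 whenever change correlates with baseline

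*SAP*

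**What the plan says.** SAP 6.1 sets the within-arm null as baseline mean minus post-baseline mean at most 0.5, "against the one-sided alternative". It states this for each arm's means, with no conditioning on baseline. SAP 6.2 turns it into a success rule for the active mask with two parts: at least two of the three graders must find the mask superior to baseline, and "the lower bound of the 95% confidence interval for the mean difference is above 0.5".

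Three places bear on how that bound is obtained:

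- SAP 6.4.2, matching protocol 8.2.1, defines a grader-averaged change for each subject and then says: "The mean change from baseline for each cell will be presented together with a two-sided 95% confidence interval". No method is named for that interval.
- SAP Appendix 1, row 1, lists "Mean efficacy change from Baseline" as an ANCOVA with skin type group and baseline mean and no treatment term. SAP 4.4 points the same way: "Model-based within-treatment and between-treatment comparisons of the efficacy variables will use the corresponding baseline value as a covariate".
- SAP 6.4.2 and protocol 8.2.1 also put the treatment means on an ANCOVA that does contain a treatment term.

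SAP 6.2 refers to none of these.

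**The concern.** The bound compared with 0.5 is the quantitative half of the only written success rule in the SAP, and it can be computed in three ways. With skin types balanced, the plain mean and the Appendix 1 least-squares mean are the same number. Their intervals are not: the ANCOVA removes the variance explained by baseline and treats the observed baseline mean as fixed. For the null in 6.1 that baseline mean is a sample quantity, and its variation belongs in the standard error.

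Two things are at stake. The same data could pass under one candidate and fail under another, with the choice still open after the data are seen. And following Appendix 1 literally can give more than the intended one-sided 2.5% error on this condition.

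**Working it through.** **Inputs.** 48 completers per arm (protocol 8.4); 8 per skin type per arm (protocol section 5); threshold 0.5 and a two-sided 95% interval, so nominal one-sided error 2.5% (SAP 6.2). The SD of change and the R² between change and baseline are not given. I take SD = 1 and vary R² from 0 to 0.50; both are assumptions.

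**Reproducing the plan's figure.** Protocol 8.4 says: "The total sample size of 96 (48 per treatment cell) completed subjects provides 92% power to detect a treatment effect of 0.7". Alpha there is 5%, two-sided. With SD = 1, z = 0.7 × √(48/2) − 1.96 = 3.43 − 1.96 = 1.47, giving 92.9% power; the noncentral t with 94 degrees of freedom gives 92.4%. The stated 92% therefore reproduces as a two-group comparison if 0.7 is standardised. This supports SD = 1 as a working unit. It says nothing about the power of the within-arm rule.

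**Error of the averaged-score condition when the true mean change is exactly 0.5.** Write σ² for the variance of change and n = 48.

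- Plain t interval: the true and the estimated variance of the mean are both σ²/n, so the error is 2.5%.
- Appendix 1 model (fitted within the arm): the estimate is still the arm mean with true variance σ²/n, but the model reports σ²(1 − R²)/n. Error = Φ(−1.96 √(1 − R²)).
- Joint model of 6.4.2, evaluated at the pooled baseline mean: the true variance is σ²(1 − R² + R²/2)/n, and the model reports about σ²(1 − R²)/n. Error = Φ(−1.96 √[(1 − R²)/(1 − R²/2)]).

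Example at R² = 0.25. Appendix 1: 1.96 × √0.75 = 1.697, error 4.5%. Joint: 1.96 × √(0.75/0.875) = 1.815, error 3.5%.

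Simulation (40,000 trials per setting, six skin types of 8, no skin-type effect), with half-widths in SD units:

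| R² | Appendix 1 error: formula / simulated | Joint error: formula / simulated | Half-width: plain / Appendix 1 / joint |
|---|---|---|---|
| 0 | 2.5% / 2.7% | 2.5% / 2.7% | 0.289 / 0.290 / 0.287 |
| 0.05 | 2.8% / 2.8% | 2.7% / 2.6% | 0.289 / 0.282 / 0.280 |
| 0.10 | 3.2% / 3.0% | 2.8% / 2.7% | 0.289 / 0.275 / 0.272 |
| 0.25 | 4.5% / 4.3% | 3.5% / 3.5% | 0.289 / 0.251 / 0.249 |
| 0.50 | 8.3% / 8.0% | 5.5% / 5.4% | 0.289 / 0.205 / 0.203 |

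The plain interval, exact for normal data, came out at 2.3% to 2.7% in the same runs, which indicates the simulation noise. If baseline and Week 12 variances are equal, R² = (1 − ρ)/2, so correlations of 0.9, 0.8 and 0.5 correspond to R² of 0.05, 0.10 and 0.25.

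**Effect on the decision.** With SD = 1 the observed improvement needed is 0.5 + 0.289 = 0.789 for the plain interval. For the Appendix 1 model it is 0.5 + 0.275 = 0.775 at R² = 0.10 and 0.5 + 0.251 = 0.751 at R² = 0.25.

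**Which covariate is responsible.** With skin type explaining 10% of the variance and baseline none, the Appendix 1 model gives 2.5%. Skin-type counts are fixed by stratification, so adjusting for them is sound. The excess comes from the baseline covariate alone.

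**Adding the grader condition** (simulated with a baseline-only ANCOVA). If a grader counts as superior when that grader's own lower bound exceeds 0, the full rule has the same error as the averaged score: 2.7% to 4.4% for R² of about 0.08 to 0.27. If the grader bound must exceed 0.5, the full rule gives 0.8% to 3.6%: below 2.5% for R² up to about 0.15, and 2.9% to 3.6% at about 0.27.

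**The case against.** A reader might infer a clean contradiction, with 6.4.2 and protocol 8.2.1 prescribing an unadjusted interval and Appendix 1 an adjusted one. The text does not support that. Neither section calls its interval unadjusted, and both go on to assess treatment means by ANCOVA. The plain interval is one natural reading of an unnamed method. The sharper textual mismatch is between the two ANCOVAs, one without a treatment term and one with.

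A reader might also infer that the trial's false-positive rate is inflated. That is not shown. The inflation needs an R² that the documents do not give, is nil at R² = 0, and is 0.3 to 0.7 percentage points at 0.05 to 0.10 under the Appendix 1 model. The figures concern one half of a two-part rule, and a strict grader threshold could bring the whole below 2.5%. SAP 6.1 also sets a two-sided active-versus-sham test, which this point does not touch.

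Finally, an adjusted mean is not an error in itself. If the target were the mean change given the enrolled women's baselines, the ANCOVA interval would be valid.

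All of this limits the size of the point but does not remove it. SAP 6.1 states no conditional target. R² is zero only if Week 12 scores regress on baseline with slope exactly 1. And because the SAP does not define superiority at grader level, the grader condition cannot be relied on to restore the error rate.

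**Conclusion.** The point holds as a defect of specification with a modest, assumption-dependent consequence. SAP 6.2 does not fix its decision interval, and the model that Appendix 1 and 4.4 attach to the within-arm mean is too narrow for the null in 6.1 whenever change correlates with baseline.

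For the averaged-score condition alone, the one-sided error against a nominal 2.5% is about 2.5% at R² = 0, 2.8% to 3.2% at 0.05 to 0.10 and 4.5% at 0.25 under the Appendix 1 model. Under the joint model the corresponding figures are 2.5%, 2.7% to 2.8% and 3.5%. These rest on an assumed R², approximately normal changes, 48 completers and, for the joint model, equal variances in the two arms. SD = 1 affects only the thresholds on the score scale, not the error rates. The error of the full rule cannot be stated from the documents. This should be corrected in the SAP; it does not call the design or the sham comparison into question.

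**What to change.** In SAP 6.2, name the decision interval for the active arm: the CI of the per-subject grader-averaged change without the baseline covariate. It can be a one-sample t interval or the CI of a skin-type-stratified mean. The stratified version avoids the conservatism of the t interval (simulated error 1.8% to 2.0% if skin type explains 10% of the variance).

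Align Appendix 1 row 1 and 4.4 with that choice for the primary within-arm decision only. The secondary variables carry no success rule, so 4.4 need not change for them. Keep the baseline-adjusted ANCOVA, with its treatment term, for active versus sham. In the same edit, state what interval and threshold make a grader's result superior, so that the error of the whole rule can be worked out.

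The cost is SAP wording, with no change to subjects, visits or data. The decision interval becomes slightly wider: with the t interval, a half-width of about 0.289 SD against 0.275 SD for the Appendix 1 model at R² = 0.10. A borderline result is therefore a little harder to pass.

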APPENDIX 2 SUMMARY TABLES

Disposition of subjects:

- Study completion status and subject evaluation

Demography and Baseline characteristics:

- Demographic and baseline characteristics, Fitzpatrick Skin Type
- Skin Type – Oiliness Level at Screening rated by subjects.

Efficacy variables:

- Fitzpatrick Wrinkle and Elastosis Scale. Analysis of the primary efficacy variable will be based on the average scores as well separately for the scores from each Expert Grader.
- Modified Griffiths Scale

■ [REDACTED]

■ [REDACTED]

Adverse events [REDACTED]:

- Summary of Adverse Events
- Summary of Treatment-Emergent Adverse Events by System Organ Class and Preferred Term
- Summary of Commonly Reported Adverse Events
- Summary of Treatment-Emergent Adverse Events by System Organ Class, Preferred Term and Severity
- Summary of Treatment Related Adverse Events by System Organ Class and Preferred Term
- Summary of Treatment Related Adverse Events by System Organ Class, Preferred Term and Severity
- Summary of Pre-Treatment Adverse Events by System Organ Class and Preferred Term
- Summary of Pre-Treatment Adverse Events by System Organ Class, Preferred Term and Severity
- Summary of Adverse Events that Resulted in Study Discontinuation
- Summary of Serious Adverse Events

■ [REDACTED]

APPENDIX 3 SUBJECT DATA LISTINGS

- Randomization code listing
- Study Completion and Subject Evaluation
- Subjects with Protocol Deviations
- Demographic and baseline characteristics
- Fitzpatrick Wrinkle and Elastosis Scale including individual mean values
- Modified Griffiths Scale including individual mean values
- [REDACTED]
- Subjects with Adverse Events
- Subjects with Serious Adverse Events
- Subjects with Adverse Events Leading to Investigational Product Withdrawn

■ [REDACTED]
